At our institute the current standardized approach is administer a perioperative prophylaxis course of ceftriaxone plus metronidazole 60 minutes prior to surgery (Figure 1). Antibiotic treatment is continued for 5-days postoperatively for patients undergoing pancreatic head resection, and the selection and duration of this specific broad-spectrum prophylactic regimen is based on recommended surgical guidelines and our own historical SSI culture data⁴³. During surgery, bile swab and aspirate samples are collected and transferred to the Pathology lab to undergo standard bile cultures and AST. If the bile cultures are eventually negative for microbial growth, the patient will be taken off the broad-spectrum antibiotics following completion of the 5-day prophylactic regimen (Figure 1). If the bile cultures are positive, then antibiotic treatment will be extended for 10 days, and therapy is tailored based on organisms and resistances identified in the bile cultures (Figure 1). Introduction of this approach in 2014 resulted in significant decrease in hospital stay, reduced the need for interventional radiology procedures, and decreased the risk of postoperative pancreatic fistula grade⁴³. Within the first year of introduction, our approach significantly decreased inpatient cost of care, decreased the total 30-day costs, and saved a total of \$1.1 million, in addition to improving patient outcome⁴³.

[figure not shown]

Figure 1: Schematic diagram of the current standardized perioperative prophylactic antibiotic treatment plan for patients undergoing total pancreatectomy and pancreaticoduodenectomy at our institution.

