Since the introduction of our standardized approach, we have improved antibiotic tailoring by developing methods of increasing detection of anaerobic species through our use of bile aspirate in addition to collection of bile swabs³⁸. However, similar to other institutions, it takes an average of 4 days for final bacterial culture results to be generated⁴⁴, and the majority of cultured microbial species have been found to exhibit multi-resistance phenotypes. This means that for the first 4-days post-surgery many of our patients at risk of developing SSI are receiving suboptimal antimicrobial therapy. This provides potential pathogens a window of opportunity to grow and propagate prior to introduction of tailored antimicrobial therapy. Rapid methods of detecting microbial species and antimicrobial resistance phenotypes are required to shorten this window of opportunity. Our data shows that in patients with positive bile cultures it took an average of 7 days to complete microbial identification and AST for bacterial and fungal species (range = 3 – 24 days), and it took 24 days to confirm the absence of biliary microbes (5 days for aerobic cultures, 14 days for anaerobic cultures, 24 days for fungal cultures). In particular, delays in detecting *Candida* species, was of concern due to the increased risk of SSI in patients with biliary candidiasis⁴⁵. In our own patient cohort, 17% of patients were positive for biliary candidiasis, and the microbe was the presumptive cause of 22% of SSIs. In patients with biliary candidiasis, it took an average length of 4.6 days for fungal identification, and an additional 6 days for anti-fungal susceptibility testing to be complete. As anti-fungals are not part of the recommended perioperative prophylactic antimicrobial treatment course, it meant that during the first 2 weeks post-surgery these patients were at increased risk of SSI due to untreated biliary candidiasis.

A single diagnostic test that would enable simultaneous identification of bacterial species (aerobic, anaerobic, fastidious), fungal species, and antimicrobial resistance in an expedited

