fashion would be highly advantageous. It would allow for all the microbial information to be generated in a single report, enabling the administration of optimal tailored antibiotics in the early postoperative window without the need for continuous changes to the treatment regimen as new information becomes available. It would also enable early cessation of antimicrobial prophylaxis if no microbes are detected, potentially reducing the complications associated with use of broad-spectrum antibiotics.

We hypothesized that use of metagenomic Oxford Nanopore (ONT) sequencing, a real-time method of sequencing that has been demonstrated to detect microbial species in as little as 6 hours^{42,46,47}, could be developed as a tool for rapid detection and characterization of biliary microbes. We have since developed methods of detecting intraoperative bile microbes, and have recently published the promising results of a prospective clinical trial that was performed to determine the feasibility and utility of ONT sequencing in detection of microbial species and antibiotic resistance genes using intra-operative bile from patients undergoing pancreatic head resection^{44,48}. Our preliminary data would suggest that not only is this technique feasible, but our ONT sequencing results highly correlate with traditional culture microbial identification and does so with a median time of 14 hours compared to 98 hours for traditional culture, a turnaround time improvement of 92%. Furthermore, the results of our study found that when standard cultures (SC) were negative (i.e. no further antibiotic therapy needed) the ONT perfectly correlated. This suggested that ONT could be used to identify patients with negative biliary microbes, enabling a more rapid cessation of unnecessary antimicrobial therapy in patients. This would improve antibiotic stewardship, a continual goal in surgical patient care.

Given these promising preliminary results, we aim to reduce the rate of SSI while minimizing overutilization of antibiotic therapy in patients undergoing pancreatic head resection by providing supplemental ONT data in addition to standard clinical cultures. This will provide not only an important potential diagnostic, but will also elucidate microbial communities within contaminated bile, potentially leading to improved targeted approaches in the future.

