1.4 Clinical Data to Date

This study will use data that has been collected under the following research study: "Comparative Analysis of Bile Microorganisms in Patients Undergoing Major Hepatobiliary Operations", IRB# 19-011419 and published in two peer-reviewed journals^{44,48}. In brief, these studies involved analysis of intraoperative bile aspirate samples collected from 42 patients undergoing pancreatic head resection (total pancreatectomy, n = 9; pancreaticoduodenectomy, n = 33) at Mayo Clinic, Rochester (see Table 1 for patient characteristics). Metagenomic ONT sequencing was performed on bile aspirates to identify microbial species (bacterial, fungal) and antibiotic resistance genes. Sequencing results were then compared to bile cultures performed as part of Mayo Clinic's standard of care clinical practice to determine how ONT sequencing compared to current 'Gold Standard' culture practices^{44,48}.

To determine the optimum ONT protocol for detection of microbial species and antibiotic resistance genes present in the bile aspirates, different methods of DNA extraction, use of host DNA depletion, and use of different AMR gene databases were evaluated⁴⁸. In total, intraoperative biliary microbes were detected in 54.7% (23/42) of patients undergoing total pancreatectomy or pancreaticoduodenectomy using SC techniques. This included 35.7% (15/42) of patients with positive bacterial cultures, 2.4% (1/42) of patients with positive fungal cultures, and 16.7% of patients with positive fungal and bacterial cultures. The male sex, use of biliary instrumentation, and performance of vascular reconstruction during surgery was significantly correlated with the detection of biliary microbes.

Table 1: Clinical characteristics of patients included in our preliminary study

Clinical feature	Total	Biliary microbes ⁺	Biliary microbes ⁻	P value
Age, mean (IQR)	61 (22 - 71)	66.3 (46.3 - 81.3)	58.0 (18 - 82.6)	0.0858
BMI, mean (IQR)	26.4 (19 - 40.4)	26.3 (19 - 40.4)	26.4 (19.7 - 36.2)	0.9295
Sex, % male (n)	54.8 (23)	38.1 (16)	16.7 (7)	0.0375
Surgery indication, % (n)				0.892
Pancreatic ductal adenocarcinoma	45 (29)	50 (21)	19.0 (8)	
Intraductal Papillary Mucinous Neoplasm	7.1 (3)	0 (0)	7.1 (3)	
Neuroendocrine tumors	11.9 (5)	2.4 (1)	9.5 (4)	
Other	11.9 (5)	2.4 (1)	9.5 (4)	
ASM Score, mean (IQR)	2.6 (1 - 4)	2.7 (2 - 4)	2.5 (1 - 3)	0.1874
Type of surgery				0.9716
Total pancreatectomy, % (n)	21 (9)	11.9 (5)	9.5 (4)	

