Pancreaticoduodenectomy, % (n)	79 (33)	42.9 (18)	35.7 (15)	
Biliary instrumentation, % (n)	52 (22)	52.4 (22)	0 (0)	<0.0001
Vascular reconstruction, % (n)	38 (16)	31.0 (13)	7.1 (3)	0.0079

BMI, body mass index; IQR, interquartile range

Comparison of our optimized ONT sequencing protocol SC results revealed that our ONT protocol had identified 100% of biliary microbial contamination cases, detected 75% of cultured bacterial species and 76% of cultured fungal species, and predicted 81% of antibiotic resistance phenotypes observed using SC results ^{44,48}. With regards to detection of common biliary pathogens ^{3,54-57}, our ONT protocol improved detection of biliary candidiasis, detected 100% of cases of biliary *Escherichia coli* and biliary *Klebsiella*, and detected 83% of biliary *Enterobacter*, 76.5% of biliary *Enterococcus*, 93.8% of biliary *Streptococcus*. However, ONT did not detect one case of *Pseudomonas* infection and one case of *Staphylococcus aureus*, indicating as proposed in this study that SC techniques should be run alongside ONT protocols to ensure that no microbial species are missed. As for detection of pathogens of high clinical concern (i.e. ESBL, CRE species), ONT similar detection rates compared to SC, and potentially improved detection of *E. coli*, *K. oxytoca*, *K. pneumoniae*, and *Citrobacter freundii*. Overall, ONT improved detection of microbial species (particularly with regards to anaerobic species and fungal species) and predicted a significantly higher number of antibiotic resistance phenotypes than were identified using SC. Significantly, the results turnaround for ONT sequencing was just 14 hours compared to an average turnaround time of 98 hours for SC. On average, it took 4.8 days (range = 1 – 15 days) to complete microbial identification and an additional 2 days (range = 0 – 9 days) to complete AST for the culture positive samples. Delays greater than 5 days in completing microbial identification occurred in samples with multiple aerobic species of the same genus (*Enterococcus* spp., *Klebsiella* spp., *Streptococcus* spp.), anaerobic species (*Schaalia (Actinomyces) turicensis*, *Finegoldia magna*, *Veillonella* sp., *Actinomyces johnsonii*, *Parvimonas micra*), and/ or fungal species *Saccharomyces cerevisiae*, *Candida* spp.), and on average, optimal antimicrobial therapy was delayed for 7 days. Use of a test that would enable microbial identification and prediction of AMR phenotypes within 24hrs post-surgery, would, therefore, have significantly shortened the delay in patients receiving optimized tailored antimicrobial therapy post-surgery.

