1.5.2 Anticipated Risks

ONT sequencing will be utilized alongside current SCs. We will use SC to ensure that the care patients receive will be no worse than current practice. In other words, culture will ensure that ONT only improves patient care and outcome. In the event that ONT results and culture assessment contradict, the care plan will prioritize the results of standard culture in the event of treatment failure (Table 3). The risks associated with participation in this study are no greater than for those patients not on the study also undergoing identical operations. The only therapeutic interventions this trial includes is alteration or cessation of postoperative antimicrobial therapy based on either ONT or SCs. In order to minimize any theoretical risks in the ONT arm, such as missed microbial species and/or antibiotic resistance phenotype or ineffective antibiotic regimen, SC data will be utilized in both arms and antibiotic therapy will be adjusted if SCs suggest broader coverage (Table 3). There will be no alteration in the standard clinical postoperative care of patients in this study.

Table 3: Incorporation of ONT results in clinical management decisions

ONT Result	Clinical management decision
A negative ONT result	Discontinue antibiotics after 24 hours of peri-operative coverage
A positive ONT result for a single pathogen typical of biliary or gastrointestinal flora	Adjust and/or narrow antibiotic therapy to cover single pathogen. If single pathogen deemed clinically insignificant (ie. lactobacillus), discontinue antibiotics after 24 hours of peri-operative coverage.
A positive ONT result for multiple pathogens	Adjust and/or narrow antibiotic therapy to cover all pathogens, excluding those deemed clinically insignificant. If all pathogens are considered clinically insignificant, discontinue antibiotics after 24 hours of peri-operative coverage.
A positive ONT result positive for rare or unexpected flora	Adjust and/or narrow antibiotic therapy to cover rare or unexpected flora, excluding those deemed clinically insignificant.
ONT results different from SC	Adjust and/or narrow antibiotic therapy to cover pathogens found in ONT results, excluding those deemed clinically insignificant. SC results to only be considered in the event of treatment failure with antibiotic therapy targeted towards ONT results.

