After sequencing data is gathered, samples will be destroyed. The data results from the ONT sequencing testing will be entered into EMR as a research clinic note for documentation and results will additionally be emailed to the medical providers on the care team. Decisions on antibiotic regimen will be made with the assistance of Surgical Clinical Pharmacy with changes in regimens as deemed appropriate based on standard cultures and ONT results, as described in Table 5. A negative ONT result will result in discontinuation of perioperative antibiotics after 24 hours while a positive ONT result will be used to guide early targeted antibiotic therapy (Table 5). With regards to early discontinuation of antibiotics, we are confident that this will not adversely impact patient care as our preliminary data demonstrated that ONT resulted in no false negative calls. However, as this is a new technology, SC will be performed alongside ONT, and if microbial growth is detected in the cultures, the clinician will have the option of reverting patient care to current standard of practice. This option will also be available in the event of treatment failure in patients with positive ONT results (Table 5).

Given that currently clinically available tests will be available to the care team with the additional ONT sequencing as supplemental data there will be minimal risk to subjects participating in this study.

Table 5 Incorporation of ONT results in clinical management decisions

ONT Result	Clinical management decision
A negative ONT result	Discontinue antibiotics after 24 hours of peri-operative coverage

A positive ONT result for a single pathogen typical of biliary or gastrointestinal flora	Adjust and/or narrow antibiotic therapy to cover single pathogen. If single pathogen deemed clinically insignificant (ie. lactobacillus), discontinue antibiotics after 24 hours of peri-operative coverage.
A positive ONT result for multiple pathogens	Adjust and/or narrow antibiotic therapy to cover all pathogens, excluding those deemed clinically insignificant. If all pathogens are considered clinically insignificant, discontinue antibiotics after 24 hours of peri-operative coverage.
A positive ONT result positive for rare or unexpected flora	Adjust and/or narrow antibiotic therapy to cover rare or unexpected flora, excluding those deemed clinically insignificant.

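### Sequencing agreement with culture does not show that stopping antibiotics at 24 hours is safe, and no listed safety check looks at the patients who stop early

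*Combined protocol and SAP*

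**What the plan says.** Usual care is set out in section 1.1. A culture-negative patient stays on prophylaxis for the full course: "the patient will be taken off the broad-spectrum antibiotics following completion of the 5-day prophylactic regimen". For the others, "If the bile cultures are positive, then antibiotic treatment will be extended for 10 days".

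Arm 2 changes this. Under Table 5 (repeated from Table 3), antibiotics stop once 24 hours of cover have been given if ONT is negative. They also stop if every organism that ONT finds is judged clinically insignificant.

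Two sentences carry the safety argument. Section 2.1 (General Design) says "we are confident that this will not adversely impact patient care as our preliminary data demonstrated that ONT resulted in no false negative calls". Section 1.5.2 says "culture will ensure that ONT only improves patient care and outcome". Both rest on the pilot of 42 patients, described in section 1.4 ("our ONT protocol had identified 100% of biliary microbial contamination cases") and in section 1.1 ("when standard cultures (SC) were negative (i.e. no further antibiotic therapy needed) the ONT perfectly correlated").

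Safety monitoring is described under Patient Follow-up and Safety Monitoring. Each row of Table 7 compares Arm 2 as a whole with Arm 1 at p<0.05 (the SSI row leaves out the threshold, but the text above the table gives it). Looks are every two weeks. The monitoring board meets six-monthly and may also stop the trial for any other safety issue it finds.

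**The concern.** A false negative here means a culture-positive patient whom ONT missed. Having none says that the two tests agree on who has contaminated bile. Whether a patient with a negative result does as well on 24 hours of antibiotics as on 5 days is a different question, and the pilot did not test it: its ONT results were only compared with culture.

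The IRB and the clinicians are therefore told not to expect harm, on evidence that does not bear on it. If SSI did rise among those who stop early, the listed rules would see it only after dilution by the rest of Arm 2.

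**Working it through.** **1. What the pilot shows.** Section 1.4 gives 23 of 42 patients culture-positive, all 23 found by ONT. The exact lower 95% limit for 23/23 is 0.025^(1/23) = 0.852, so sensitivity against culture is 100% (85% to 100%). At species level, section 1.4 reports that 75% of cultured bacterial species were found.

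**2. Outcome data on 24-hour cover.** The documents report none. The outcome gains cited in section 1.1 belong to the existing pathway (5 days, longer if culture-positive) and are not split by culture result. Section 1.4 says only that the two tests did not differ in identifying patients at risk of SSI.

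**3. Whether culture is a safeguard.**
- *Negative on both tests:* culture never prompts action, yet cover falls from 5 days to 24 hours. The statement in section 1.5.2 cannot hold for this patient.
- *ONT-negative, culture-positive:* the texts disagree. The last row of Tables 3 and 5 looks to culture only after treatment failure. The Arm 2 description in section 2.1 lets a positive culture direct therapy instead of ONT. The text before Table 5 makes a return to usual care the clinician's option.
- *Timing:* section 1.4 gives an average of 98 hours, with identification taking 1 to 15 days. Supplement S2 has plates first read after at least 16 hours, so growth may show sooner. No single delay describes this.

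**4. What the whole-arm SSI rule would see.** Inputs:
- 70 per arm (section 6.1);
- SSI 9/42 = 0.2143 at 30 days (section 1.4), used for every group without harm;
- ONT-negative share from 1 − 0.77 = 0.23 to 1 − 0.54 = 0.46 (section 6.1 positivity rates for ONT and for culture), or about 16 to 32 of 70 patients.

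The harm, +20 points in ONT-negative patients and none elsewhere, is illustrative.

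Arm 2 rate = 0.2143 + share × 0.20:
- share 0.23: 0.2143 + 0.046 = 0.260
- share 0.46: 0.2143 + 0.092 = 0.306

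The rule fires when z = (p₂ − p₁)/√(2p̄(1 − p̄)/70) exceeds 1.96. One look was enumerated over all pairs of binomial counts. Two-weekly looks were simulated: 40,000 trials, 52 looks (2 years, section 1.6) from 10 to 70 per arm, outcomes known at once.

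| Scenario | One look, z test | One look, Fisher | Two-weekly looks, z test |
|---|---|---|---|
| No harm | 2.6% | – | 11.4% |
| +20 points, share 0.23 | 9.5% | 6.4% | 24.4% |
| +20 points, share 0.46 | 23.9% | 17.9% | 42.5% |

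**5. A comparable group in both arms.** Only Arm 2 is sequenced, so ONT-negative patients have no randomised counterpart. Unstented patients do: stenting is a stratification factor in sections 2.1, 4.2 and 5.2. Section 1.4 also reports that "use of biliary instrumentation, and performance of vascular reconstruction during surgery was significantly correlated with the detection of biliary microbes". From Table 1, 42 − 22 = 20 patients were not instrumented, of whom 19 were culture-negative (95%, CI 75% to 100%).

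Taking instrumentation as a stand-in for stenting, about 20/42 × 70 = 33 patients per arm would be unstented. If all ONT-negative patients are among them, 16/33 = 48% to 32/33 = 97% of unstented Arm 2 patients would stop early. The same +20-point harm would then reach two-sided 0.05 at one look in about 15% to 41% of trials, against 9.5% to 23.9% for the whole arm.

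Precision remains poor. The half-width 1.96 × √(2p(1 − p)/n) is about 20 to 22 points for n = 32 or 33 per arm and SSI of 21.4% to 26.3%.

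**The case against.** The strongest reply is that protection already exists. Patients are watched round the clock as inpatients, SSI is assessed daily, looks are two-weekly, the board may act on any safety issue, and the primary endpoint itself requires a non-significant effect on SSI. A site safety-monitoring plan is mentioned in section 7.2 (Medical Monitoring), and its report layout is not in these documents. All of that stands. It limits the monitoring gap to what the visible protocol lists, but it does not support either risk sentence.

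Whole-arm SSI is also a sensible measure, because ONT-positive patients could be harmed by narrowing. And the step 4 calculation models only the SSI row; the abscess, morbidity and mortality rows could fire too. Both points are fair. The share of 23% to 46% is not an upper bound either: patients whose organisms are all judged insignificant also stop at 24 hours, so dilution may be smaller than shown.

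The proposed table is noisy and sets no threshold. True, and for that reason it should be read as descriptive.

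A reader might infer from the pilot counts that patients with negative bile did worse, since only 4 of the 9 SSI patients were positive on both tests. That would be 5/19 against 4/23 (Fisher p = 0.71). The counts cannot bear this: moving one patient gives 4/19 against 5/23 (p = 1.00), culture-positive patients had longer tailored courses, and nobody is reported as having had 24-hour cover. They show neither safety nor harm and are not used as evidence here.

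A reader might also subtract 24 from 98 and say that culture rescue comes up to 74 hours late. That treats an average as a maximum; the real delay may be near zero or more than a week.

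**Conclusion.** The point holds and is minor. The stated confidence rests on agreement with culture, which does not address SSI after 24 hours of cover, and the documents offer no other evidence. The assurance in section 1.5.2 is untrue for patients negative on both tests and unsettled for those ONT-negative and culture-positive.

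On monitoring, a 20-point SSI rise confined to ONT-negative patients would trigger the whole-arm SSI rule in about 24% to 43% of trials with two-weekly looks (9% to 24% at one look), where 11% would trigger with no harm. This rests on the pilot SSI rate applying to every group without harm, an ONT-negative share of 23% to 46%, immediate outcomes, and a harm size chosen for illustration.

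It would go too far to conclude that the 24-hour rule is unsafe, or that early stoppers go unmonitored. The documents support neither: the effect is unknown, and general monitoring is in place.

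**What to change.** 1. In each monitoring-board report, show SSI and organ-space SSI by arm, with counts and confidence intervals, in (a) patients without a biliary stent and (b) culture-negative patients. Mark (b) as provisional, since in the sponsor's own data "it took 24 days to confirm the absence of biliary microbes". Add the SSI count among all Arm 2 patients stopped at 24 hours for any Table 5 reason, and the number who were ONT-negative and culture-positive. These are descriptive items, with no new p<0.05 rule.
2. In section 2.1, replace the sentence expressing confidence with: *In the pilot ONT was positive in all 23 culture-positive patients (95% CI 85-100%). The effect on SSI of stopping at 24 hours is not known and will be reviewed by the DSMB.*
3. In section 1.5.2, replace the assurance about culture with: *Culture cannot protect a patient negative on both tests whose antibiotics stop at 24 hours; if ONT is negative and culture is positive, culture guides therapy.* Align the last row of Tables 3 and 5 with the Arm 2 description in section 2.1.

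The cost is two sentences, one table row and one report table, from data that sections 5.2 and 5.3 already collect. No patients, samples or staff are added, and the 24-hour rule for a negative ONT result stays. The downsides are a less favourable risk statement and a noisy table. The unstented group is itself diluted if ONT positivity is 77%, when about half of it would not stop on a negative result.
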